- 1) To compare adherence among persons across the three study arms.
- 2) To evaluate the safety, tolerability and acceptability of treatment in the three arms.

3. Background

Globally, an estimated 70 – 80 million persons are chronically infected with hepatitis C (HCV). Chronic hepatitis C is associated with long-term complications including liver cirrhosis, hepatocellular carcinoma and end-stage liver disease. Chronic hepatitis C is treatable and treatment can cure infection such that HCV RNA is undetectable and persons cannot transmit virus and risk for chronic complications decreases substantially. Treatment access has been hampered in much of the world in part due to the low efficacy and toxicity of the previous generation of regimens. The landscape of HCV treatment has changed dramatically over the past few years with the FDA approval of highly efficacious, non-toxic second generation direct acting antiviral agents. With these advances in treatment, questions have arisen about delivery of these agents among populations in resource-limited settings (RLS) given some of the inherent differences in HCV infected patients in these settings. Ideally, a treatment regimen for RLS should be pan-genotypic; thereby, not requiring HCV genotype testing which can be cost prohibitive and rarely available in these settings. Moreover, treatment delivery strategies need to optimize adherence particularly in populations that have had suboptimal adherence such as people who inject drugs (PWID).

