All subjects will complete screening, baseline, end-of treatment and post-treatment assessments. All of these assessments will take place in the YRG-JHU ICC in Bilaspur. Screening assessments will be completed within 28 days of the Baseline/Day 1 visit. Participants in all three arms will be asked to complete 4 study visits: 1) Screening; 2) the Baseline/Day 1 of treatment visit; 3) End of treatment visit (at 4 weeks for participants in Arm 1 and at 12 weeks for participants in Arms 2 and 3); and 4) 12 weeks post treatment completion visit (SVR12). In addition, subjects in Arm 1 will need to visit the clinic for an additional 3 visits to receive their PEG injections and participants in Arm 3 will need to come in at Weeks 4 and 8 for medication refills. Finally, subjects in Arms 1 and 2 will receive daily visits from field staff to receive their study medications.

The details of procedures at each visit are listed below. Information on laboratory parameters to be measured and details regarding the clinical assessments that will be performed are provided in 4a5.6.

4a3. Screening and Consent Procedures

Subjects will complete all screening assessments within 28 days of the Baseline/Day 1 visit. Written informed consent will be obtained from subjects prior to the assessment of study eligibility. Those who fail to satisfy eligibility criteria for the trial will still be able to receive services provided by the ICC. If they are still visiting the ICC, they will be allowed to re-screen for the pilot trial if they were excluded because of a modifiable exclusion criteria (e.g., Platelet count <50,000 cells/ml).

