Moderate	Decrease PEG dose 50%	Evaluate once weekly by clinician at visit and daily recording of symptoms by outreach worker in field	Consider psychiatric consultation. Continue reduced dosing.	If symptoms improve and are stable for 4 weeks, may resume normal visit schedule. Continue reduced dosing or return to normal dose.	(See severe depression)
Severe	Discontinue PEG permanently	Immediate psychiatric consult with CIMS	Psychiatric therapy as necessary as supervised by physician at CIMS		

Table 2. Procedures for Dose modification for serious adverse events related to hematologic abnormalities

Laboratory values		Pegylated Interferon $\alpha 2a$
Hgb	<10.0 g/ dl	---
	<8.5 g/dl	Permanently discontinue
WBC	<1.5 x 10 ⁹ /L	Reduce dose by 50%
	<1.0 x 10 ⁹ /L	Permanently discontinue
Neutrophil	<0.75 x 10 ⁹ /L	Reduce dose by 50%
	<0.5 x 10 ⁹ /L	Permanently discontinue
Platelets	<50 x 10 ⁹ /L	Reduce dose by 50%
	<25 x 10 ⁹ /L	Permanently discontinue
Bilirubin – direct	2.5 x ULN*	Permanently discontinue
Bilirubin – indirect	>5 mg/dl	
	>4 mg/dl (for 4 weeks)	Permanently discontinue
Creatinine	> 2 mg/dl	Permanently discontinue
ALT/AST	2 x baseline and 10 x ULN	Permanently discontinue

*ULN = upper limit of normal

Treatment interruption

We will track missed doses using our biometric system in Arms 1 and 2. Participants who miss ≥ 1 but fewer than 2 weeks of doses will have their treatment extended so that they complete the total number of doses in their assigned arm (e.g., 28 for Arm 1 and 84 for Arm 2). If a client misses 2 weeks or more of therapy,

treatment will be restarted in its entirety at the discretion of the study physician and in consultation with the participant. Treatment can only be restarted one time. If there is a second interruption of >2 weeks, treatment will not be restarted. Participants in Arm 3 will be counseled to complete all doses of medications even if it takes longer than 84 days (e.g., 94 days). If participants in Arm 3 report an interruption >2 weeks at their 4-weekly medication refill visit, they will also be provided with one opportunity to restart treatment for the entire duration of 12 weeks at the discretion of the study clinician as with Arms 1 and 2.

4a5.3. End of Treatment Visit

The following procedures/assessments will be completed at the End of Treatment Visit

- Obtain vital signs
- Assessment of adverse events and concomitant medications

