All analyses will be conducted as intention to treat. We will use a chi-squared test of proportions to compare the proportions that achieve SVR12. Pairwise comparisons with correction for multiple comparisons will be conducted to directly compare Arms 1 and 2, Arms 1 and 3 and Arms 2 and 3. For secondary outcomes, chi squared tests of proportions will be used to compare categorical outcomes and a Wilcoxon rank-sum test will be used to compare adherence.

The primary objective of this study is to test the feasibility of DOT for HCV treatment among HCV-infected persons with substance use history in a resource limited setting. An additional objective is to generate pilot data to plan a larger powered study. We hypothesize that SVR12 will be higher in Arm 1 compared to Arms 2 and 3. Assuming a two-sided $\alpha=0.05$, 50 people in each arm and 70% achieving SVR12 in Arm 3, we will have >80% power to detect a difference of 25% (e.g., 95% completion in the SOF+DAC+PEG).

No interim analyses will be conducted as with 150 participants, it will not be possible to observe statistical differences prior to the completion of the trial.

d. Early stopping rules.

As we do not plan to do interim analyses, the only reason for stopping the trial would be a higher frequency than expected of serious adverse events. We will continually monitor the frequency of serious adverse events and if this frequency is 10% or higher, we will prematurely stop the trial.

8. Risks

a. Medical risks, listing all procedures, their major and minor risks and expected frequency.

It is anticipated that most participants who complete their full course of treatment with optimal adherence will clear hepatitis C from their bodies. However, for those individuals who do not respond to treatment, it is possible that non-response will affect their ability to respond to other drugs for hepatitis C in the future. However, with the newer direct acting antiviral (DAA) regimens, response rates have been demonstrated to be comparable in treatment naïve and prior non-responders. The primary risk related to taking these medications is with respect to side effects associated with pegylated interferon alfa2a.

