Safeguards will also be taken to ensure that subjects' confidentiality is maintained. These measures include: 1) unique study numbers in databases and on specimens; 2) maintaining identifiers separately in a password protected database (utilizing two levels of password security); 3) restricting access to locked files and password protected databases to essential study personnel. All data will be reported in aggregate form only without personal identifiers. In the case of an adverse event, policies and procedures are in place to work with the subject and to keep the study's governing bodies informed

The study doctor and study staff will monitor participants for any signs of new or unexpected side effects at weekly study visits for Arm 1 and during daily visits in the field for Arms 1 and 2. Participants will be informed to contact the study doctor if they have side effects or are unable to perform daily functions. They will be given contact phone numbers and a means to SMS outreach workers in order to report side effects. In addition, the field workers who will be delivering SOF and DAC in the field will be trained to ask questions about side effects to capture any potential problems in real time. A detailed list of potential side effects and their relative frequency will be included on the consent form.

Our study team, including our doctors and outreach workers, has been working with drug users for the past 3

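### Side effects are asked about daily in Arms 1 and 2 but at no scheduled point in Arm 3 between Baseline and End of Treatment, which biases the comparison of symptom-based adverse events

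*Combined protocol and SAP*

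**What the plan says.** **Active enquiry.** Section 8b has the study doctor and staff monitor for "side effects at weekly study visits for Arm 1 and during daily visits in the field for Arms 1 and 2". The workers who deliver the daily doses "will be trained to ask questions about side effects to capture any potential problems in real time". Arm 3 has no directly observed therapy (DOT), so these workers do not see it.

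**Arm 3 contacts on treatment.** Section 4a2 says that "participants in Arm 3 will need to come in at Weeks 4 and 8 for medication refills". No procedures are listed for those visits. The one thing that the plan expects to learn there is a missed stretch of treatment (section 4a5.2, Treatment interruption): "If participants in Arm 3 report an interruption >2 weeks at their 4-weekly medication refill visit".

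**Scheduled AE assessment.** It is listed at Screening, Baseline, End of Treatment and any Early Termination visit (sections 4a3, 4a5.1, 4a5.3 and 4a5.4).

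**Passive route, all arms.** Section 8b: "Participants will be informed to contact the study doctor if they have side effects or are unable to perform daily functions". Phone numbers and an SMS route are provided.

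**Use of the data.** Secondary objective 2 is "To evaluate the safety, tolerability and acceptability of treatment in the three arms". Section 7b defines an any-AE outcome from a list of interferon side effects, most of them subjective, such as fatigue, headache, insomnia and nausea. Under section 7c, "chi squared tests of proportions will be used to compare categorical outcomes".

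**The concern.** Whether a mild or passing symptom enters the record depends heavily on whether someone asks and how soon. Here the intensity of asking is fixed by the randomised arm. Randomisation balances true risk between arms but does nothing for this, because the difference arises after allocation and is part of the delivery model.

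The problem is sharpest for Arm 2 v Arm 3. The drugs and the 12-week course are the same, so this is not a matter of unequal follow-up time. A headache in Week 2 has a good chance of being recorded in Arm 2 the same day. In Arm 3 it must be volunteered by phone or SMS, or remembered about ten weeks later. DOT delivery could then look less tolerable than self-administration of identical drugs. That comparison should inform the larger study for which this pilot is meant to supply data.

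In Arm 1 v Arm 3, more frequent asking adds to whatever interferon truly causes, and the analysis in section 7c cannot separate the two.

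**Working it through.** The plan gives no figure on this point, so there is none to reproduce. Its one power statement concerns SVR12 and is unaffected.

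**Step 1. Scheduled enquiries on treatment, if every planned contact takes place**

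| | Arm 1 (4 weeks) | Arm 2 (12 weeks) | Arm 3 (12 weeks) |
|---|---|---|---|
| Daily field contacts | about 28 | about 84 | 0 |
| Weekly clinic visits for injections | yes | no | no |
| AE assessment listed at Weeks 4 and 8 | not applicable | no clinic visit | none listed |
| End of Treatment assessment | 1 | 1 | 1 |

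Over the same 12 weeks and the same drugs, Arm 2 has up to 84 field enquiries before its End of Treatment assessment and Arm 3 has none.

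**Step 2. From capture to observed proportions**

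Let *t* be the true risk of at least one symptom-based AE, equal in Arms 2 and 3, and let *c*₂ and *c*₃ be the shares of affected people whose event is recorded. The observed proportions are *t·c*₂ and *t·c*₃, and the spurious difference is *t*(*c*₂ − *c*₃).

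From the documents: n = 50 per arm and two-sided α = 0.05 (section 7c states these for SVR12; they are carried over to the AE test). Assumed, because the documents give no values: *t* = 10%, 20% or 40%; *c*₂ = 90%; *c*₃ = 70%, 60% or 50%.

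**Step 3. Chance of a false Arm 2 v Arm 3 difference**

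For every pair of counts (*a*, *b*) from 0 to 50, the Pearson statistic is X² = (*a*/50 − *b*/50)² / [*p̄*(1 − *p̄*)(2/50)], with *p̄* = (*a* + *b*)/100. The rejection rate is the sum of the binomial probabilities of all pairs with X² ≥ 3.841.

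| True risk | Observed in Arm 2 | Observed in Arm 3 at 70 / 60 / 50% capture | Spurious difference (points) | False-positive rate |
|---|---|---|---|---|
| 10% | 9% | 7 / 6 / 5% | 2 / 3 / 4 | 6 / 8 / 11% |
| 20% | 18% | 14 / 12 / 10% | 4 / 6 / 8 | 9 / 14 / 22% |
| 40% | 36% | 28 / 24 / 20% | 8 / 12 / 16 | 14 / 26 / 43% |

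With 90% capture in both arms, the rate is about 5% at each of the three risks.

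**Step 4. Effect of a multiplicity correction**

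Section 7c describes its pairwise correction in connection with SVR12. If a Bonferroni level of 0.05/3 were also used here, the 40% row would become 6 / 14 / 27%, against 1.7% with equal capture. The correction lowers the error rate but leaves the bias in place.

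**The case against.** **Arm 3 is not unobserved.** It has the phone and SMS route, two refill visits at which staff could ask, and an assessment at any early termination; section 8c1 also requires AEs to be recorded throughout the study. All of this is correct. But the passive route is open to every arm and so does not offset daily asking in two of them. The rule in section 8c1 says what to record, not when to ask. Asking at refill visits is not written into the plan.

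**SOF and DAC side effects are described as rare (section 8a).** This bears on the size, which is why the table starts at a 10% risk, where the inflation is modest. It does not remove the problem. The AE definition in section 8c1 does not require causation, and the listed symptoms are common for other reasons.

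**Two stronger readings are tempting, and the documents support neither.**

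- A reader might infer that secondary objective 2 cannot be answered. Deaths, hospitalisations and discontinuations depend far less on daily questions, and Table 3 schedules blood counts, liver and renal tests at the same visits in every arm. Description within each arm also remains possible.
- A reader might infer that the whole safety comparison only measures how often people were asked. That comes close only for symptoms in Arm 2 v Arm 3. Arm 1 v Arm 3 also contains a possible interferon effect. In Arm 1 v Arm 2 both arms are asked daily, and the larger difference is 4 v 12 weeks of observation.

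**Testing only on a checklist could create a new imbalance.** This stands for a checklist given once in Arm 1 and three times in Arms 2 and 3, and for dropping events found at injection visits from the report. The fix below is built to avoid both.

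**Conclusion.** The concern holds for non-serious, symptom-based AEs. If the plan is followed as written, Arm 2 v Arm 3 is biased towards more AEs in Arm 2, and Arm 1 v Arm 3 is confounded by frequency of asking. The direction requires only that daily asking captures more than one recall at Week 12 supplemented by self-report.

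The size is uncertain. Over the assumed range, the false-positive rate for Arm 2 v Arm 3 runs from 6% to 43% against about 5% with equal capture. The upper end needs both a 40% true risk and only 50% capture in Arm 3. Serious events leading to hospitalisation or death, and scheduled laboratory results, are much less affected, and the primary outcome is not touched. The change should be made because it is cheap and also closes a 12-week gap in which Arm 3 is never scheduled to be asked about harms.

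**What to change.** 1. **Visits.** List an AE assessment at Arm 3's existing Week 4 and Week 8 refill visits in section 4a2 and Table 3.
2. **Instrument.** Use one structured AE checklist with the same recall period at Weeks 4, 8 and 12 in Arms 2 and 3. In Arm 2 the field worker gives it where there is no clinic visit. In Arm 1, give it at End of Treatment. Section 4a2 puts that visit at 4 weeks and the Table 3 footnote at 5; these must be reconciled so that the recall windows match.
3. **Analysis (section 7c).** Base the Arm 2 v Arm 3 test of symptom-based AEs on checklist events over Weeks 0–12. Base comparisons of Arm 1 with Arms 2 and 3 on the checklist covering the first 4 weeks only, so that each arm compared has the same number of enquiries.
4. **Reporting.** Report AEs from every source, including daily DOT and weekly injection visits, by arm as a descriptive analysis, and state that all-source differences reflect unequal ascertainment.

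**Cost.** A few minutes at contacts that already take place and a short addition to section 7c; no new visits or staff. AEs found only in the field or at injection visits are described rather than tested. Some imbalance will remain, because the person asking differs between Arms 2 and 3 and daily questioning may sharpen recall. The checklist reduces the bias but does not guarantee its removal.
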